#### **5.2.4.2    Prohibited Concomitant Therapies for Patients with PHN**

Concomitant use of the following therapies is prohibited from the screening (Visit 1) through post-treatment follow-up (Visit 11). After informed consent is obtained, subjects who are under treatment with the following prohibited concomitant therapies will undergo a washout period of 7 days or more. Visit 1 will occur after completion of this washout period.

- 1) Nerve blocks
- 2) Iontophoresis
- 3) Laser therapy
- 4) Acupuncture treatment
- 5) Spinal cord stimulation
- 6) Surgery that may confound the assessment of PHN
- 7) Transcutaneous electrical nerve stimulation
- 8) Other forms of pain reduction therapy for PHN (except for psychological therapy, mental therapy, and physical therapy [eg, massage, kinesiology, heat treatment, and cryotherapy])

### **5.2.5 Restricted Concomitant Therapies for Patients with PHN**

The following therapies are permitted for concomitant use if their frequency has not changed for 14 days prior to Visit 1. These drugs may be used concomitantly from the screening (Visit 1) through the post-treatment follow-up (Visit 11), but the dosage may not be changed.

- 1) Psychological therapy
- 2) Mental therapy
- 3) Physical therapy (eg, massage, kinesiology, heat treatment, and cryotherapy)

### **5.2.6 Other**

Subjects should be instructed to avoid excessive consumption of alcohol during the treatment period, as the investigational product may increase side effects of sleepiness and dizziness and potentiate the impairment of motor skills.

## **6. STUDY PROCEDURES**

A study visit schedule in tabular format is provided in Section 17.1.

In principle, all of the activities and/or examinations will be recorded with the date in the CRF.

Missing visits are strongly discouraged in this study. It is expected that investigator site staff thoroughly explain the visit schedule to potential subjects. If it is felt that a subject is not able to adhere to the visit schedule, then that subject should not be enrolled into the study. Any missed visit that occurs during the this study must be rescheduled within 1 week.

### **6.1 Screening (Visit 1, 7 days prior to initiation of study treatment)**

Written informed consent will be obtained before screening. For subjects with DPNP, if prohibited concomitant drugs are used within 7 days before obtaining informed consent, screening activities will follow a washout period of at least 7 days. For subjects with PHN, if prohibited concomitant drugs or prohibited concomitant therapies are used within 7 days before obtaining informed consent, screening activities will follow a washout period of at least 7 days. Therefore, in this case, written informed consent must be obtained before entering the washout period. The following activities and/or examinations will be performed at screening.

For patients with DPNP and patients with PHN:

- Evaluate inclusion criteria and exclusion criteria
- Record demographics (birth date, sex), medical/surgical history related to exclusion criteria and alcohol history
- Provide explanation regarding electronic patient diary, and provide electronic diary
- Complete SF-MPQ
- Complete HADS
- Measure body height and weight
- Perform physical examination
- Perform evaluation of edema
- Perform ophthalmologic examination
- Measure blood pressure and pulse rate

- Perform 12-lead ECG
- Collect blood and urine samples for laboratory tests
- Evaluate AEs
- Complete C-SSRS
- Perform pregnancy test (only in women of childbearing potential)
- Evaluate prior drug treatment, concomitant drugs, and concomitant therapy
- Complete Module A and B on MINI Interview (Version 6.0)

For patients with DPNP only:

- Record demographics specific for patients with DPNP (type of diabetes, duration of diabetes, duration of DPN, duration of DPNP)
- Perform full neurological examination
- Collect blood sample for evaluation of HbA1c
- Collect blood sample for evaluation of fasting blood glucose levels

For patients with PHN only:

- Record demographics specific for patients with PHN (site of herpes zoster skin rash, onset date and recovery date for current herpes zoster skin rash, duration of PHN, the site of PHN [trigeminal segment area, cervical segment area, thoracic segment area, lumbar segment area, and sacral segment area])

## **6.2 Initiation of Study treatment (Visit 2, Day 1)**

At the beginning of the titration period, the following activities and/or examinations will be performed and 2.5 mg BID of DS-5565 will be issued to the subjects with moderate renal impairment (CrCL: 30-59 mL/min) or 2.5 mg QD of DS-5565 will be issued to the subjects with severe renal impairment (CrCL: 15-29 mL/min).

For patients with DPNP and patients with PHN:

- Evaluate inclusion criteria and exclusion criteria
- Review electronic patient diary data
- Complete SF-MPQ
- Complete HADS

- Measure body weight
- Perform physical examination
- Perform abbreviated neurological examination
- Measure blood pressure and pulse rate
- Collect blood and urine samples for laboratory tests
- Evaluate AEs
- Complete C-SSRS
- Record and evaluate concomitant drugs and concomitant therapy
- Issue the investigational product
- Select and record the drug administration in the morning (fasted/fed) during the study treatment (for only the subjects with moderate renal impairment)

For patients with PHN only:

- Perform full neurological examination

### **6.3 Treatment Period**

The treatment period will be 14 weeks in duration.

#### **6.3.1 Visit 3 and Visit 4**

From Visit 2 to Visit 4, subjects will come to the study site every week (Visit 3, Visit 4). The investigator or sub-investigator will confirm tolerability and review continuation of the treatment before issuing the new investigational product. The following activities and/or examinations will be performed at Visit 3 and Visit 4.

For patients with DPNP and patients with PHN:

- Review electronic patient diary data
- Complete SF-MPQ
- Complete HADS
- Measure body weight
- Perform physical examination
- Perform abbreviated neurological examination
- Measure blood pressure and pulse rate

- Collect blood and urine samples for laboratory tests
- Evaluate AEs
- Complete C-SSRS
- Record and evaluate concomitant drugs and concomitant therapy
- Collect unused investigational product, and record and review drug-taking compliance
- Record the date of the first dose taken
- Issue the investigational product
- Collect blood sample for PK analysis

#### **6.3.2 Visit 5, Visit 6, Visit 7, Visit 8, and Visit 9**

From Visit 4 to Visit 9, subjects will come to the study site once every 2 weeks (Visit 5, Visit 6, Visit 7, Visit 8, and Visit 9). The investigator or sub-investigator will confirm tolerability and review continuation of the treatment before issuing the new investigational product. The following activities and/or examinations will be performed at Visit 5, Visit 6, Visit 7, Visit 8, and Visit 9.

For patients with DPNP and patients with PHN:

- Review electronic patient diary data
- Complete SF-MPQ
- Complete HADS
- Measure body weight
- Perform physical examination
- Perform abbreviated neurological examination
- Measure blood pressure and pulse rate
- Collect blood and urine samples for laboratory tests
- Evaluate AEs
- Complete C-SSRS
- Record and evaluate concomitant drugs and concomitant therapy

- Collect unused investigational product, and record and review drug-taking compliance
- Issue the investigational product
- Collect blood sample for PK analysis (Visit 5 and Visit 6 only)

For patients with DPNP only:

- Collect blood sample for evaluation of HbA1c (Visit 6 only)
- Collect blood sample for evaluation of fasting blood glucose levels (Visit 6 only)

#### **6.4 End of Treatment/Early Termination (Visit 10)**

The treatment period will be completed at Visit 10. The following activities and/or examinations will be performed at the end of treatment/early termination.

For patients with DPNP and patients with PHN:

- Collect and review electronic patient diary data, and collect electronic diary
- Complete SF-MPQ
- Complete PGIC
- Complete HADS
- Measure body weight
- Perform physical examination
- Perform evaluation of edema
- Perform full neurological examination
- Perform ophthalmologic examination
- Measure blood pressure and pulse rate
- Perform 12-lead ECG
- Collect blood and urine samples for laboratory tests
- Complete C-SSRS
- Perform pregnancy test (only in women of childbearing potential)
- Evaluate AEs
- Record and evaluate concomitant drugs and concomitant therapy

- Collect unused investigational product, and record and review drug-taking compliance
- Record the date of the last dose taken

For patients with DPNP only:

- Collect blood sample for evaluation of HbA1c
- Collect blood sample for evaluation of fasting blood glucose levels

For patients with PHN only:

- Perform abbreviated neurological examination

#### **6.5 Post-treatment Follow-up (Visit 11, 7 days after the completion of administration)**

Follow-up observations will be conducted 7 days after the completion of administration (Visit 11). The following activities and/or examinations will be performed at post-treatment follow-up.

For patients with DPNP and patients with PHN:

- Complete HADS
- Measure body weight
- Perform physical examination
- Perform abbreviated neurological examination
- Measure blood pressure and pulse rate
- Collect blood and urine samples for laboratory tests
- Evaluate AEs
- Complete C-SSRS
- Record and evaluate concomitant drugs and concomitant therapy

## **7. EFFICACY ASSESSMENTS**

### **7.1 Efficacy Variable(s)**

#### **1) Pain score**

Each subject will record a pain score in the electronic patient diary once daily from the day after Visit 1 through Visit 10. Every morning upon awakening, prior to taking study medication, the subject will select the number that best describes his or her pain over the past 24 hours on a scale of 0 (no pain) to 10 (worst possible pain). ADPS is the weekly average pain score based on the pain scores from the electronic patient daily pain diaries.

#### **2) Short-Form McGill Pain Questionnaire**

At Visit 1, Visit 2, Visit 3, Visit 4, Visit 5, Visit 6, Visit 7, Visit 8, Visit 9, and Visit 10, subjects will provide a self-assessment using the SF-MPQ. The SF-MPQ consists of 3 parts:

- Fifteen pain descriptors that are given a score of 0 (none) to 3 (severe) based on intensity. The scores are summarized as a sensory score of 11 descriptors, an affective score of 4 descriptors, and a total score of 15 descriptors.
- A VAS, in which the subject rates pain intensity on a 100 mm-long horizontal line, where 0 mm = no pain and 100 mm = worst possible pain.
- A Present Pain Intensity index that provides a score of 0 to 5 based on intensity

#### **3) Patient Global Impression of Change**

At Visit 10, subjects will provide a self-assessment in comparison to Visit 2, using the 7-point scale in the PGIC.

1: very much improved

2: much improved

3: minimally improved

4: no change

5: minimally worse

6: much worse

7: very much worse

4) Sleep-interference Score

The Daily Sleep Interference Diary consists of an 11-point NRS which will be used to assess how pain has interfered with the subject's sleep during the past 24 hours. Each subject will record a sleep-interference score in the electronic patient diary once daily from the day after Visit 1 through Visit 10. Every morning upon awakening, prior to taking study medication, the subject will select the number that best describes his or her sleep interference experience during the past 24 hours on a scale of 0 (pain did not interfere with sleep) to 10 (pain completely interfered with sleep). The weekly average sleep interference score is based on the sleep interference scores from the electronic patient daily pain diaries.

## **8. PHARMACOKINETIC AND BIOMARKER ASSESSMENTS**

### **8.1 Pharmacokinetic Variable(s)**

As part of this study, blood samples from subjects will be collected for PK analysis.

These blood samples will be collected at the following visits:

Visits 3, 4, 5 and 6 (Weeks 1, 2, 4 and 6)

Blood samples will be collected in accordance with the procedures described in Section 17.2.

#### **8.1.1 For the Subjects with Moderate Renal Impairment**

At the visits specified above, PK samples will be collected before the morning dose of study medication and 1 ( $\pm 0.5$ ) hour after the morning dose. The subject will be instructed 1 visit before the scheduled visit for PK sampling not to take study medication before coming to the site.

In the CRF, the following will be recorded:

- Administration/No administration in the morning on the day before each visit
- Administration/No administration at bedtime on the day before each visit
- Administration/No administration in the morning on the day of each visit
- Date/Time of the morning dose on the day before each visit
- Date/Time of the bedtime dose on the day before each visit
- Date/Time of the morning dose on the day of each visit
- Taking/No taking breakfast on the day of each visit
- Date/Time of breakfast on the day of each visit
- Date/Time of blood sampling before the morning dose
- Date/Time of blood sampling 1 hour after the morning dose

#### **8.1.2 For the Subjects with Severe Renal Impairment**

At the visits specified above, PK samples will be collected 1 time.

In the CRF, the following will be recorded:

- Administration/No administration at bedtime on the day before each visit
- Date/Time of the bedtime dose on the day before each visit

- Date/Time of blood sampling

## **8.2 Biomarker Variable(s)**

No biomarker analysis will be performed.

## 9. SAFETY ASSESSMENTS

Safety endpoints will be body weight, AEs, laboratory values, vital sign, 12-lead ECG, findings from physical examination, findings from neurological examination, C-SSRS, HADS, edema, and findings from ophthalmologic examination.

### 9.1 Adverse Events

#### 9.1.1 Definition of Adverse Event

An AE is any unfavorable and unintended sign (including an abnormal laboratory value or abnormal vital sign), symptom, or disease that develops after the subject signs the Informed Consent Form (ICF) and up to 7 days after the last dose of study medication (Visit 11), regardless of relationship to the investigational product.

Any symptom that the investigator or sub-investigator considers associated with DPN will be evaluated as an efficacy variable and will not be regarded as an AE. However, if the symptom is considered potentially related to the investigational product, such symptom will be regarded as an AE. If any pre-existing symptom or disease is aggravated during the study period, the aggravation will be reported as an AE, and the date of confirming the aggravation will be considered the date of event onset.

Dizziness, somnolence, edema, and weight increase are currently defined as “significant AEs”. Any other significant AEs to be added will be specified in the statistical analysis plan (SAP).

All antiepileptic drugs carry a risk of increased suicidal behavior and ideation. Furthermore, increased hepatic transaminases have been observed in the DS-5565 development program. Therefore, the following “suicidal behavior and ideation” and “liver enzyme elevations/liver dysfunction” will be treated as AEs of special interest.

- Increase in ALT or AST  $\geq 5 \times$  ULN
- ALT or AST rises to  $\geq 3 \times$  ULN and persists for more than 2 weeks
- Concurrent increases in ALT or AST  $\geq 3 \times$  ULN and T-Bil  $\geq 2 \times$  ULN
- ALT or AST  $\geq 3 \times$  ULN associated with a clinical presentation suggestive of liver injury (ie, including the appearance of fatigue, nausea, vomiting, jaundice, right upper quadrant pain or tenderness, fever, rash, and/or eosinophilia)
- Serious hepatobiliary AE
- Severe hepatobiliary AE

- Hepatobiliary AE leading to discontinuation
- Any transaminase elevation associated with a clinical presentation suggestive of liver injury
- An elevation of ALT or AST  $\geq 3 \times$  ULN (without clinical presentation suggestive of liver injury)
- AE related to suicide (if there are any “yes” responses to any of the questions in the C-SSRS)

#### **9.1.2 Items to Be Investigated Concerning Adverse Events**

If an AE develops during the clinical study, the items in Table 9-1 will be investigated and the results will be recorded. The subject should be questioned in a general way, without asking about the occurrence of any specific symptoms.

Table 9-1: Items to be Investigated for Adverse Event

Items reviewed	Content of review	
Content of AE	Name of AE, date of onset	
Action taken regarding the investigational product	None	No change in investigational product dosage was made.
	Discontinued	The investigational product was permanently stopped.
	Permanently	
	Interrupted	The investigational product was temporarily stopped.
Outcome	Dose Reduced	The dosage of the investigational products was reduced.
	Classification of outcome, date of outcome assessment, date of resolution	
	Classification of outcome	
 
Recovered/Resolved
 

	Recovered/Resolved with Sequelae	
 
The subject fully recovered from the AE, with no residual effects observed.
 
The residual effects of the AE are still present and observable.
 
Identify sequelae/residual effects.
 

Severity	Not Recovered/Not Resolved	
 
Identify sequelae/residual effects.
 
The AE itself is still present and observable.
 

	Recovering/Resolving	
 
The AE was almost fully resolved, and the subject recovered to near-baseline status.
 

	Unknown	
 
No information and the outcome was unknown.
 

	Fatal	
Seriousness	Mild	Awareness of sign or symptom, but easily tolerated, ie, does not interfere with subject's usual function
	Moderate	Discomfort enough to cause interference with usual activity
	Severe	Incapacitating with inability to work or do usual activity, ie, interferes significantly with subject's usual function
Definition of SAE	Serious (according to the following definition of SAEs) / Not serious	
	
 
1. Results in death
 
2. Life-threatening
 
3. Requires inpatient hospitalization or prolongation of existing hospitalization
 
4. Results in persistent or significant disability/incapacity
 
5. A congenital anomaly/birth defect
 
6. An important medical event
 
	

Table 9-1: Items to be Investigated for Adverse Event (cont.)

Items reviewed	Content of review
Relationship to the investigational product	Classification of relationship (in accordance with the following classifications of relationship), reason for that assessment
Classification of relationship	
Related
 
 
• The AE follows a reasonable temporal sequence from investigational product administration, and cannot be reasonably explained by the subject's clinical state or other factors (eg, disease under study, concurrent diseases, concomitant medications).
 
• The AE follows a reasonable temporal sequence from investigational product administration, and is a known reaction to the drug under study or its chemical group, or is predicted by known pharmacology.
 
 
Not related
 
 
• The AE does not follow a reasonable temporal sequence from investigational product administration, or can be reasonably explained by the subject's clinical state or other factors (eg, disease under study, concurrent diseases, concomitant medications).
 

Other action taken for event	
None
 
No treatment was required.
 
Medication required
 
Prescription and/or over-the-counter medication was required to treat the AE.
 
Hospitalization or prolongation of hospitalization required
 
Hospitalization was required or prolonged due to the AE, whether or not medication was required.
 
Other

SAE = serious adverse event

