### **2.2 Study Hypothesis**

The primary hypothesis of this open-label study is that DS-5565 will be generally safe and well-tolerated when the drug is administered with a dosing of 7.5 mg BID in subjects with moderate renal impairment (Creatinine Clearance [CrCL]: 30-59 mL/min) and 7.5 mg QD in subjects with severe renal impairment (CrCL: 15-29 mL/min).

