#### **4.2.1 Withdrawal Criteria**

If a subject meets the following withdrawal criteria, that subject should be withdrawn from the study.

- Difficulty of continuing the study due to AE
- Subjects with any of the following elevations in clinical laboratory values
  - Increase in ALT or AST  $\geq 5 \times$  ULN
  - ALT or AST rises to  $\geq 3 \times$  ULN and persists for more than 2 weeks
  - Concurrent increases in ALT or AST  $\geq 3 \times$  ULN and total bilirubin (T-Bil)  $\geq 2 \times$  ULN
  - ALT or AST  $\geq 3 \times$  ULN associated with a clinical presentation suggestive of liver injury (ie, including the appearance of fatigue, nausea, vomiting, jaundice, right upper quadrant pain or tenderness, fever, rash, and/or eosinophilia)
- Decrease in CrCL  $< 15$  mL/min
- AE related to suicide (if there are any "yes" responses to any of the questions in the C-SSRS)
- Withdrawal by subject (ie, withdrawal of consent)
- Major deviation from study procedure

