##### 5.1.2.1 Dosing Regimens for the Subject with Moderate Renal Impairment

During the treatment period, 1 tablet (for titration period) or 2 tablets (for fixed dose period) DS-5565 will be administered orally twice daily (in the morning and at bedtime). The subject must select the administration timing, either fasted or fed in the morning at initiation of study treatment (Visit 2), and it will be followed during the treatment period.

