### 5.1.2.2 Dosing Regimens for the Subject with Severe Renal Impairment

During the treatment period, 1 tablet (for titration period) or 2 tablets (for fixed dose period) DS-5565 will be administered orally once daily at bedtime.

Table 5-1: Method of Administration During the Treatment Period

	Day 1		Day 2 to 7		Day 8		Day 9 to 14		Day 15		Day 16 to 98		Day 99	
	Morning	Bedtime	Morning	Bedtime	Morning	Bedtime	Morning	Bedtime	Morning	Bedtime	Morning	Bedtime	Morning	Bedtime
Moderate renal impairment (CrCL: 30-59 mL/min)	—	2.5	2.5	2.5	2.5	5	5	5	5	7.5	7.5	7.5	7.5	—
Severe renal impairment (CrCL: 15-29 mL/min)	—	2.5	—	2.5	—	5	—	5	—	7.5	—	7.5	—	—

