### 5.1.3 Method of Assessing Treatment Compliance

All subjects in this study will commence therapy as outpatients, and the investigational product will be self-administered orally. Subjects will take home with the investigational product. Each subject is to return the investigational product at every visit. Compliance will be assessed by returned tablet count. Administration of the investigational product will be recorded in the eCRF/Drug Accountability Record (number of tablets taken) at all treatment visits. If no tablets are returned, the subject will be asked whether any were discarded or thrown away, or if all of the tablets were taken orally.

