## **11.7 Safety Analyses**

### **11.7.1 Adverse Event Analyses**

All AEs will be coded using the Medical Dictionary for Regulatory Activities (MedDRA). Any AEs that appear after the first administration or that worsen relative to the pre-treatment state are considered as TEAEs.

The number and percentage of subjects reporting TEAEs will be calculated for the categories listed below by CrCL group and all-DS-5565 treatment. The number and percentage of subjects reporting TEAEs and ADRs will be summarized by system organ class, preferred term, and CrCL group and all-DS-5565 treatment.

- TEAE
- ADR
- Serious TEAE
- Serious ADR
- Severe TEAE
- Severe ADR
- Significant TEAE
- Significant ADR
- TEAE leading to treatment discontinuation
- ADR leading to treatment discontinuation

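### The AE form records dose reduction and interruption, but no planned summary shows which subjects left the assigned regimen that way without stopping

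*Combined protocol and SAP*

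**What the plan says.** **Recording.** Table 9-1 in Section 9.1.2 offers four actions on the investigational product: none, permanent discontinuation, interruption ("The investigational product was temporarily stopped") and dose reduction ("The dosage of the investigational products was reduced").

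**Dosing.** Section 5.1.2.1 prescribes for moderate impairment "1 tablet (for titration period) or 2 tablets (for fixed dose period) DS-5565 will be administered orally twice daily". Section 5.1.2.2 prescribes for severe impairment "1 tablet (for titration period) or 2 tablets (for fixed dose period) DS-5565 will be administered orally once daily at bedtime". Tables 5-1 to 5-3 give the matching schedule and packs. None of these states whether a dose may be lowered, paused or resumed.

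**Routes off the regimen.** Section 4.2.1 lists as a ground for withdrawal "Difficulty of continuing the study due to AE". Sections 6.3.1 and 6.3.2 ask the investigator to check tolerability and decide on continuation at each visit; they name no other step.

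**Analysis.** Section 11.7.1 lists ten categories: any, serious, severe, significant and discontinuation-leading events, each for TEAEs and for ADRs. Only the last pair rests on action taken, for example "TEAE leading to treatment discontinuation". Section 11 plans no summary of exposure or compliance, although Section 5.1.3 says that administration "will be recorded in the eCRF/Drug Accountability Record (number of tablets taken) at all treatment visits".

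**Question.** The primary endpoint (Section 3.1.3.1) is safety and tolerability. The hypothesis (Section 2.2) is that "DS-5565 will be generally safe and well-tolerated when the drug is administered with a dosing of 7.5 mg BID" in moderate impairment, and likewise at 7.5 mg QD in severe impairment.

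**The concern.** The hypothesis is about tolerability at a named dose. In a single-arm, descriptive study, the natural evidence on that is how many subjects could not stay on the dose because of adverse events. There are three ways to leave it: stop, pause or step down. The form captures all three, and the planned summaries single out only the first.

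A subject with moderate dizziness whose drug was paused would fall into the same listed categories as a subject with mild dizziness and no action: any TEAE, significant TEAE and, if judged related, ADR. A reader of the report would have the discontinuation percentage as the only action-based measure and could take it as the whole of dose-limiting intolerance. An error from that source can run only in the favourable direction, because adding a category of affected subjects cannot lower the count.

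The silence of the dosing sections is a second, smaller problem. With an action on the form and no rule in the dosing text, sites may handle the same event differently.

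**Working it through.** **1. The plan's own figure.** Section 11.11 asks for 30 subjects to see at least one moderate or severe dizziness or somnolence event with 95% probability at a 10% rate. P(at least one) = 1 − 0.9^n. For n = 29 this is 95.3%, and for n = 30 it is 95.8%. The figure reproduces and is not in dispute. The number enrolled is about 35.

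**2. Where a reduced or paused subject appears.** Take each Section 11.7.1 category in turn, counting TEAE and ADR together:

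| Category | Includes the subject? | Shows that the drug was reduced or paused? |
|---|---|---|
| Any TEAE / ADR | Yes (ADR if related) | No |
| Serious | Only if serious | No |
| Severe | Only if severe | No |
| Significant | Only if a listed event (Section 9.1.1) or one the SAP adds | No |
| Leading to discontinuation | Only if later stopped for the event | No |

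The subject is counted, but the action taken is visible nowhere.

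**3. Weight of one subject.** Assume all 35 are dosed and so enter the safety analysis set. One subject is 1/35 = 2.9 percentage points. Results are also given by CrCL group, whose sizes the plan does not state. If the severe group held 5 to 15 subjects (assumed), one subject would be 1/15 = 6.7 to 1/5 = 20 points of that group.

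**4. Is it likely to arise?** The plan gives no rate. For assumed rates p of reduction or interruption for an event, the expected number is 35p and P(at least one) = 1 − (1 − p)^35:

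| Assumed p | Expected subjects | P(at least one) |
|---|---|---|
| 5% | 1.75 | 83.4% |
| 10% | 3.5 | 97.5% |
| 20% | 7 | 99.96% |

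**5. Illustration of the effect.** Assume 2 subjects discontinue for a TEAE and k different subjects are only reduced or paused. Exact binomial 95% intervals are in brackets:

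| k | Planned table shows | Combined count shows |
|---|---|---|
| 2 | 2/35 = 5.7% (0.7 to 19.2) | 4/35 = 11.4% (3.2 to 26.7) |
| 4 | 2/35 = 5.7% (0.7 to 19.2) | 6/35 = 17.1% (6.6 to 33.6) |

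The counts in steps 4 and 5 are assumptions chosen to show scale; they are not predictions.

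**The case against.** The case on the other side has real force on several points.

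- *The events are not hidden.* Every reduced or paused subject with a TEAE is in the overall table and in the tables by system organ class and preferred term. Dizziness, somnolence, edema and weight increase are significant events whatever was done with the drug. This stands. A reader might infer that the TEAE tables count only discontinuations; they do not. Only the breakdown by action taken is missing.
- *Nobody is labelled as tolerating the dose.* A reader might infer that these subjects will be reported as tolerating 7.5 mg. The documents define no such status or rate, so the subjects are unidentified, not misclassified.
- *Table 9-1 records; it does not authorise.* This stands. A form that can capture a departure from the regimen does not contradict the regimen, and the options may be a generic list. The dosing text neither permits nor forbids reduction, so the fault there is silence.
- *A detailed SAP is to follow (Section 11.2).* It was not available for this review and may add the category. But Section 9.1.1 expressly leaves further significant events to the SAP, whereas Section 11.7.1 presents its categories as a complete list with no such opening.
- *Not every pause is intolerance.* Some TEAEs are unrelated to the drug, and a subject paused and later stopped for an event is already counted. This stands, and it is why an ADR row and a combined count without double counting are needed.

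Two further inferences are not supported. A tablet count that mixes 2.5 mg and 5 mg tablets would obscure the dose taken, but the documents do not show the layout of the accountability form. Nor does any section attribute Week 14 pain to uninterrupted dosing; that analysis is secondary and descriptive.

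**Conclusion.** The point holds as a gap in reporting on the primary question. If Section 11.7.1 is followed as written, the study report will not show how many subjects left the assigned regimen by reduction or interruption for an adverse event, so the discontinuation rate alone can understate intolerance of that regimen.

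The size cannot be known from the documents. It is 2.9 percentage points for each affected subject not otherwise counted as a discontinuation, assuming 35 dosed, and more within a CrCL group. If no subject is reduced or paused, the effect is zero. The data are collected, so nothing is irrecoverably lost; what is missing is the commitment to report them.

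**What to change.** 1. Reconcile Table 9-1 with Section 5.1.2 and Tables 5-1 to 5-3, so that the protocol states the position on reduction and interruption. Which text governs is for the sponsor to decide, and no dosing rule is proposed here.
2. Whatever is decided, add two categories to Section 11.7.1: *TEAE leading to dose interruption or reduction* and *ADR leading to dose interruption or reduction*.
3. Add a combined count of subjects with discontinuation, interruption or reduction for a TEAE, and the same for an ADR, each subject counted once.
4. Present all of these by CrCL group and overall, from the Table 9-1 action field.

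The cost is a wording change in the protocol or SAP and a few table rows, with no new data collection. The tolerability figure may look less favourable.
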